### **1.3 EFFICACY ENDPOINTS**

#### **Overall response rate (ORR)**

ORR is defined as sum of CR and PR rates.

#### Progression-free survival (PFS)

PFS is defined as the interval from registration to the earlier of the first documentation of definitive disease progression or death from any cause.

Definitive disease progression based on standard criteria (Hallek et al. 2018) and occurring for any reason (i.e., increasing lymphadenopathy, organomegaly or bone marrow involvement; decreasing platelet count, hemoglobin, or neutrophil count; or worsening of disease-related symptoms) other than lymphocytosis.

#### Complete Response (CR) Rate

CR rate is defined as the proportion of patients who achieve a CR.

####  Minimal Residual Disease (MRD) Negativity Rate

MRD negativity rate is defined as the proportion of patients who are MRD negative.

#### Duration of response (DOR)

DOR is defined as the interval from the first documentation of CR or PR to the earlier of the first documentation of definitive disease progression or death from any cause.

# 3. ELIGIBILITY CRITERIA

Patients must meet all of the following inclusion criteria and none of the exclusion criteria to be eligible for participation in this study.

## 3.1 INCLUSION CRITERIA

Patients must meet all of the following inclusion criteria to be eligible for participation in this study:

- 1) Have a diagnosis of B-cell CLL that has not been previously treated and now warrants treatment consistent with accepted iwCLL criteria (Hallek 2018) for initiation of therapy. Any one of the following conditions constitute CLL that warrants treatment:
  - a) Evidence of progressive marrow failure as manifested by the onset or worsening of anemia and/or thrombocytopenia, or
  - b) Massive (i.e., lower edge of spleen ≥ 6 cm below the left costal margin), progressive, or symptomatic splenomegaly, or
  - c) Massive (i.e., ≥ 10 cm in the longest diameter), progressive, or symptomatic lymphadenopathy, or
  - d) Progressive lymphocytosis in the absence of infection, with an increase in blood absolute lymphocyte count (ALC) >50% over a 2-month period or lymphocyte doubling time of <6 months (as long as initial ALC was  $\geq$  30,000/µL), or
  - e) Autoimmune anemia and/or thrombocytopenia that is poorly responsive to corticosteroids or other standard therapy, or
  - f) Symptomatic or functional extranodal involvement (e.g. skin, kidney, lung, or spine), or
  - g) Constitutional symptoms, defined as any one or more of the following diseaserelated symptoms or signs occurring in the absence of evidence of infection:
    - i) Unintentional weight loss of  $\geq 10\%$  within the previous 6 months, or
    - ii) Significant fatigue (≥ Grade 2), or
    - iii) Fevers >100.5°F or 38.0°C for  $\ge$ 2 weeks, or
    - iv) Night sweats for >1 month.
- 2) Adequate organ system function, defined as follows:
  - a) Absolute neutrophil count (ANC)  $\geq$  1,000/mm^3 platelet count  $\geq$  30,000/mm^3, (ANC  $\geq$  500/mm^3 and platelet count  $\geq$  20,000/mm^3 permitted if known marrow involvement). Growth factors are permitted at any time during the study, but not to meet eligibility criteria.
  - b) Total bilirubin ≤1.5 times the upper limit of normal (ULN) (unless diagnosed with Gilbert's syndrome).
  - c) Alanine aminotransferase (ALT) and aspartate aminotransferase (AST) ≤2.5 x ULN if no liver involvement or ≤5 x the ULN if known liver involvement
  - d) Calculated creatinine clearance >30 mL/min (as calculated by the Cockcroft-Gault or MDRD formula, 24 hour urine Cr clearance also acceptable)
- 3) ECOG performance status  $\leq 2$
- 4) Male or female  $\geq$  18 years of age
- 5) Ability to swallow and retain oral medication
- 6) Female patients who are not of child-bearing potential and female patients of childbearing potential who have a negative serum pregnancy test within 3 days prior to Cycle 1, Day 1. Female patients of child-bearing potential and all male partners, and male patients must consent to use a medically acceptable method of contraception

throughout the study period and for 30 days after the last dose of study drug.

7) Willingness and ability to comply with trial and follow-up procedures, and give written informed consent

#### 3.2 EXCLUSION CRITERIA

Patients who meet any of the following exclusion criteria are not to be enrolled to this study:

- 1) Has ever received any form of treatment for CLL.
- Corticosteroid therapy of prednisone > 10 mg or equivalent started at least 7 days prior to Cycle 1, Day 1 is prohibited. Prednisone ≤ 10 mg daily or equivalent is allowed as clinically warranted. Topical or inhaled corticosteroids are permitted.
- 3) Prior treatment with umbralisib.
- 4) Prior treatment with autologous hematologic stem cell transplant or prior Allogeneic hematologic stem cell transplant is excluded.
- 5) Evidence of chronic active Hepatitis B (HBV, not including patients with prior hepatitis B vaccination; or positive serum Hepatitis B antibody) or chronic active Hepatitis C infection (HCV), active cytomegalovirus (CMV), or known history of HIV. If HBc antibody is positive the subject must be evaluated for the presence of HBV DNA by PCR. If HCV antibody is positive, the subject must be evaluated for the presence of HCV RNA by PCR. See Appendix C. If the subject is CMV IgG or CMV IgM positive, the subject must be evaluated for the presence of CMV and negative HBV DNA by PCR. Subjects with positive HBc antibody and negative HBV DNA by PCR are eligible. Subjects with positive HCV antibody and negative HCV RNA by PCR are eligible. Antiviral prophylaxis should be considered per institutional protocol.
- 6) Known histological transformation from CLL to an aggressive lymphoma (i.e. Richter's transformation / Hodgkin Lymphoma).
- 7) Evidence of ongoing systemic bacterial, fungal or viral infection, except localized fungal infection of skin/nails. NOTE: Subjects may be receiving prophylactic antiviral or antibacterial therapies at investigator discretion. Use of anti-pneumocystis and antiviral prophylaxis is required.
- 8) Inflammatory bowel disease (such as Crohn's disease or ulcerative colitis)
- 9) Malabsorption syndromes
- 10) Irritable bowel syndrome with greater than 3 loose stools per day as a baseline.
- 11) Any severe and/or uncontrolled medical conditions or other conditions that could affect their participation in the study such as:
  - a) Symptomatic, or history of documented congestive heart failure (NY Heart Association functional classification III-IV) See Appendix B
  - b) Myocardial infarction within 6 months of enrollment
  - c) Concomitant use of medication known to cause QT prolongation or torsades de pointes should be used with caution and at investigator discretion.
  - d) Angina not well-controlled by medication
  - e) Poorly controlled or clinically significant atherosclerotic vascular disease including cerebrovascular accident (CVA), transient ischemic attack (TIA), symptomatic peripheral arterial disease, angioplasty, cardiac/vascular stenting within 6 months of enrollment.
- 12) Malignancy, including myelodysplastic syndromes, within 3 years of study enrollment

except for basal, squamous cell carcinoma or melanoma in situ, carcinoma in situ of the cervix, superficial bladder cancer not treated with intravesical chemotherapy or BCG within 6 months, localized prostate cancer following curative treatment and with a normalPSA level

- 13) Women who are pregnant or lactating.
- 14) Subjects requiring immediate cytoreductive therapy.

# 4. STUDY DESIGN

#### 4.1 OVERVIEW OF STUDY DESIGN

This study is designed as a Phase 2, single-center, single-arm trial to evaluate the ORR and PFS of umbralisib in treatment naïve CLL patients requiring therapy. Daily doses of oral umbralisib will be administered in the absence of disease progression, unacceptable toxicity, or withdrawal from treatment. Treatment cycles are 4 weeks, with the efficacy evaluations within 14 days prior to Cycle 4, Day 1 for Cycle 3 assessment, and within 14 days prior to Cycle 13, Day 1 for Cycle 12 assessment, and at any other time point to confirm progression. Patients who fail to achieve a partial or complete response to umbralisib at the Cycle 3 assessment will discontinue study treatment. At that time, patients- will be provided appropriate options to receive established frontline therapy. Patients who demonstrate a partial or complete response will be treated until disease progression, unacceptable toxicity, or the end of the study. Enrollment will be up to 35 patients.

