## 9 STATISTICAL CONSIDERATIONS

#### 9.1 SAMPLE SIZE

This is a phase 2 study designed to assess the overall response rate (CR + PR) and progressionfree survival (PFS) of Umbralisib in treatment naïve patients with CLL. The primary endpoint is the overall response rate (ORR) from the time of treatment. The study will plan to enroll up to 40 subjects, and assuming 10% attrition, the study will have approximately 35 subjects remaining for analysis. Any subjects who are screen failures are not considered enrolled and may be replaced to meet the accrual goal. Enrollment is expected to be completed in approximately 18 months with 24 months follow up. The ORR for the standard of care is about 60%. We expect that Umbralisib treatment could lead to 80% ORR. A Simon 2-stage minimax design that differentiates ORRs of 0.60 (null hypothesis) and 0.80 (alternative hypothesis) will be used to assess treatment efficacy, with the probabilities of a type I error (falsely accepting a non-promising therapy) and type II error (falsely rejecting a promising therapy) both set at 0.10. Twenty seven patients will be accrued in the first stage of the study. If 18 or fewer patients have a response, then the study will be terminated and declared negative. If 19 or more patients have a response, then an additional 8 patients will be accrued to the second stage. At the conclusion of the study, if 25 or more patients have a response out of a total of 35 patients enrolled, the regimen will be considered worthy of further investigation.

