#### 9.3 STUDY POPULATIONS

Two study populations, intent-to-treat (ITT) and safety populations, are pre-defined for this study. The ITT population will include all enrolled patients who provide some efficacy assessments and the safety population will include all patients who take at least one dose of study medication. The efficacy analyses will be based on ITT population and the safety analyses will be based on the safety population.

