#### 9.7 EFFICACY ANALYSES

Each patient will be assigned to one of the following categories: 1) complete response, 2) partial response, 3) stable disease, 4) progressive disease, 5) early death from malignant disease, 6) early death from toxicity, 7) early death because of other cause, or 8) unknown (not assessable, insufficient data).

Many of the efficacy measures will be based on disease assessments. The best clinical response as well as disease progression will be determined by the treating investigator. Scans should be kept on file in cases where independent review or confirmation may be warranted. Definitive disease progression will be based on standard criteria (Hallek et al. 2018) occurring for any reason (e.g., increasing lymphadenopathy, organomegaly or bone marrow involvement; decreasing platelet count, hemoglobin, or neutrophil count; or worsening of disease-related symptoms) other than lymphocytosis.

During the study period, all patients will be evaluated for response by CT or MRI within 14 days prior to Cycle 4, Day 1 for Cycle 3 assessment, and within 14 days prior to Cycle 13, Day 1 for Cycle 12 assessment, and at any other time point to confirm progression. Patients who fail to achieve a partial or complete response to umbralisib at the Cycle 3 assessment will discontinue study treatment. At that time, patients- will be provided appropriate options to receive established frontline therapy. Patients who demonstrate a partial or complete response will be treated until disease progression, unacceptable toxicity, or the end of the study.

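### Enrolment is capped at 35 in section 4.1 but at 40 in the synopsis and 9.1, and the decision rule uses 35 both before and after attrition

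*Combined protocol and SAP*

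**What the plan says.** The current text gives two enrolment ceilings.

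- Section 4.1: "Enrollment will be up to 35 patients".
- Section 9.1, and the statistics part of the synopsis in the same terms: "The study will plan to enroll up to 40 subjects, and assuming 10% attrition", which is said to leave approximately 35 for analysis.

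The decision rule follows directly in the synopsis and 9.1. Stage 1: "Twenty seven patients will be accrued in the first stage of the study", with a stop at 18 or fewer responses. With 19 or more, "then an additional 8 patients will be accrued to the second stage". The regimen is judged worthy of further study "if 25 or more patients have a response out of a total of 35 patients enrolled".

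Three other statements bear on who is counted.

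- On replacement, 9.1 says: "Any subjects who are screen failures are not considered enrolled and may be replaced to meet the accrual goal". It is silent on enrolled patients who later cannot be assessed.
- Section 9.3 defines the efficacy population: "The ITT population will include all enrolled patients who provide some efficacy assessments".
- Section 9.7 begins its classification with "Each patient will be assigned to one of the following categories". The list includes three kinds of early death and an unknown category.

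Section 9.8 adds that, apart from partial dates, missing data are not imputed.

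**The concern.** The number 35 has two incompatible roles. In 4.1 and in the final rule it is a count of patients enrolled. In the attrition sentence it is what remains of 40 after losses. Screen failures cannot bridge the gap, because 9.1 says they do not count as enrolled.

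The go/no-go decision rests on 19 of 27 and 25 of 35, and the design has almost no spare power at 35. A team working from 4.1 would close accrual at 35 enrolled, lose some patients, and judge the remainder against a cut-off set for 35. The text also does not say whether the 27 in stage 1 are enrolled or assessable, so the interim decision has the same ambiguity.

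**Working it through.** **Inputs** (section 9.1 and synopsis): null ORR 0.60, alternative 0.80, both error rates 0.10, stage 1 n = 27 (continue at 19 or more), stage 2 n = 8, success at 25 or more of 35, attrition 10%. Caps: 35 (4.1) and 40 (synopsis, 9.1).

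**Step 1: reproduce the plan's design.** With N analysed in total and response rate p,

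P(success) = Σ over x = 19 to 27 of P[Bin(27, p) = x] × P[Bin(N − 27, p) ≥ 25 − x].

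At N = 35 this gives 0.0965 for p = 0.60 (limit 0.10) and 0.9003 for p = 0.80 (target 0.90). A full search over two-stage designs confirms that 35 is the smallest feasible total and that this is the minimax design. The design reproduces.

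**Step 2: check the attrition arithmetic.** 35 / 0.9 = 38.9, so 39 enrolled would be needed; 40 is consistent with that. A cap of 35 leaves 35 × 0.9 = 31.5.

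**Step 3: performance at other analysed numbers,** cut-offs 19 and 25 kept and 27 evaluable in stage 1:

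| N analysed | Type I error | Power |
|---|---|---|
| 31 | 0.0126 | 0.571 |
| 32 | 0.0248 | 0.698 |
| 33 | 0.0444 | 0.800 |
| 34 | 0.0697 | 0.866 |
| 35 | 0.0965 | 0.9003 |
| 36 | 0.121 | 0.916 |

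**Step 4: cap of 35 with 10% loss.** Assume independent loss and that lost patients leave the denominator, as 9.3 and 9.8 suggest. The number evaluable is then Binomial(35, 0.9). Weighting power at 0.80 by its probabilities, for N = 28 to 35:

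0.0352 × 0.160 + 0.0765 × 0.284 + 0.1376 × 0.428 + 0.1998 × 0.571 + 0.2247 × 0.698 + 0.1839 × 0.800 + 0.0973 × 0.866 + 0.0250 × 0.900 ≈ 0.611.

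N of 27 or fewer adds about 0.001. Average power is 0.612, with average type I error 0.026.

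**Step 5: 40 enrolled, decision on the first 35 evaluable, cut-off 25 kept if fewer.** The number evaluable is Binomial(40, 0.9), so P(35 or more) = 0.794 and P(fewer than 35) = 0.206.

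- Power: 0.794 × 0.9003 + 0.1068 × 0.866 + 0.0576 × 0.800 + 0.0264 × 0.698 + 0.0104 × 0.571, plus about 0.002 for N of 30 or fewer, ≈ 0.879.
- Type I error: 0.794 × 0.0965 + 0.1068 × 0.0697 + 0.0576 × 0.0444 + 0.0264 × 0.0248 + 0.0104 × 0.0126 ≈ 0.087.

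**The case against.** The best reply is that the intention is plain: enrol up to 40 so that about 35 can be analysed, with 27 + 8 as the decision set. That is the natural reading of the synopsis and 9.1, and it performs acceptably (step 5). But 4.1 still sets a different ceiling, the final rule still says enrolled, and no passage states that the first 35 evaluable patients form the decision set.

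A reader might infer more than the documents support.

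- *That with 40 enrolled, either type I error exceeds 0.10 or power falls well below 0.90.* Step 5 shows otherwise. The 0.121 at N = 36 requires more patients than the 27 + 8 in 9.1, so it is a misapplication to guard against and not the plan's error rate.
- *That losses count as non-responders.* With 35 enrolled this would give power 0.567, but it rests mainly on the word enrolled in the rule. Sections 9.3 and 9.8 point the other way. The figure also assumes that 60% and 80% are rates among assessable patients only, which the documents do not say.
- *That 9.3 and 9.7 flatly contradict each other.* One defines a population and the other lists outcome categories, and a patient with some assessment can still have insufficient data. The real gap is patients who die or leave before any assessment.
- *That 40 × 0.9 = 36 against approximately 35 is an error.* It is rounding.

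**Conclusion.** The concern holds as a conflict between two enrolment caps and an undefined denominator. The Simon design is not at fault.

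Under the cap in 4.1 and the plan's own attrition, power averages about 0.61 (0.571 with 31 evaluable, 0.698 with 32), against the stated 0.90. This rests on independent 10% loss, lost patients leaving the denominator, 27 evaluable patients in stage 1, and cut-offs of 19 and 25. Under the cap of 40 with the decision taken on the first 35 evaluable, the shortfall is small: power about 0.88 and type I error about 0.087. The text should be corrected before the rule is applied, because choosing the denominator once responses are known would undermine control of the error rates.

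**What to change.** 1. State one enrolment cap, 40, in the synopsis, 4.1 and 9.1.
2. Replace the word enrolled in the decision rule. State that 27 and 35 are the first 27 and first 35 response-evaluable patients in enrolment order, so that nobody beyond the 35th enters the test.
3. State, for analysis only, that treated patients who die, progress or stop for toxicity before the Cycle 3 assessment count as evaluable non-responders. Only patients who cannot be assessed for unrelated reasons leave the denominator. Align 9.3 and 9.7 with this.
4. Keep the cut-off of 25 if fewer than 35 are evaluable. State that with 40 enrolled and a full 10% uninformative loss, type I error is about 0.087 and power about 0.88. Power is nearer 0.90 if fewer patients are lost that way, provided 80% is the rate among all evaluable patients, including those counted as non-responders under item 3.

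If the cap of 35 is kept instead, restate power under 10% attrition as about 0.61.

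The cost is wording. No patients are added beyond the 40 already planned, and stated power falls from 0.90 to about 0.88.

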#### 4.2 REGISTRATION/ENROLLMENT

Following Screening, qualified patients will receive the following:

• Umbralisib 800 mg once daily

During the study period, all patients will be evaluated for response by CT or MRI within 14 days prior to Cycle 4, Day 1 for Cycle 3 assessment, and within 14 days prior to Cycle 13, Day 1 for Cycle 12 assessment, and at any other time point to confirm progression. Patients who fail to achieve a partial or complete response to umbralisib at the Cycle 3 assessment will discontinue study treatment. At that time, patients- will be provided appropriate options to receive established frontline therapy. Patients who demonstrate a partial or complete response will be treated until disease progression, unacceptable toxicity, or the end of the study.

#### 4.3 STUDY SITES

This is a single-center study. Enrollment is expected to be completed in approximately 18 months.

#### 4.4 DISCONTINUATION FROM STUDY TREATMENT

Patients will be discontinued from study treatment for any of the following reasons:

- Disease progression
- Failure to achieve a partial or complete response to umbralisib at the Cycle 3 assessment
- Intolerable toxicity related to study drug
- Patient requests to withdraw consent or discontinue treatment
- Pregnancy
- Inability of the patient to comply with study requirements
- Conditions requiring therapeutic intervention not permitted by the protocol
- Non-compliance/lost to follow-up
- Investigator discretion
- Discontinuation of the study

Patients who discontinue from study treatment prior to Cycle 12 (for reasons other than progressive disease) should continue to be followed for progression approximately every 3 months up until the time Cycle 12 would have occurred, then approximately every 6 months.

Patients who discontinue from study treatment after Cycle 12 for reasons other than disease progression should be followed for progression approximately every 6 months.

After withdrawal from protocol treatment, patients should be followed for AEs for 30 calendar days after their last dose of study drug. All new AEs occurring during this period must be reported and followed until resolution, unless, in the opinion of the investigator, these values are not likely to improve because of the underlying disease. In this case the investigators must record his or her reasoning for this decision in the patient's medical records.

All patients who have CTCAE Grade 3 or 4 laboratory abnormalities at the time of withdrawal should be followed until the laboratory values have returned to Grade 1 or 2, unless in the opinion of the investigator, it is not likely that these values are to improve because of the underlying disease. In this case, the investigator must record his or her reasoning for making this decision in the patient's medical records.

All patients that begin therapy outside of the scope of this protocol within 30 days of discontinuing umbralisib do not need to be followed for AEs, unless umbralisib is determined to be the direct cause of the AE in the opinion of the treating investigator. After 30 days from discontinuation of umbralisib, these AEs no longer need to be followed.

# 5. STUDY ASSESSMENTS AND TREATMENT SCHEDULE

The table below lists all required assessments that should be performed at each study visit.

| All cycles are 28 day cycles | Screening  |    | Сус | le 11 |     | Cycles 2 - 6  | > Cycle 6  | End of    | F/U | End of |
|------------------------------|------------|----|-----|-------|-----|---------------------------|------------------------|-----------|-----|--------|
| The cycles are 20 day cycles | D-28 to D0 | D1 | D2  | D8    | D15 | D1                        | Every 3 cycles         | Treatment | 1/0 | Study  |
| Medical History              | Х          |    |     |       |     |                           |                        |           |     |        |
| ECOG Performance Status      | Х          | Х  |     |       |     |                           |                        |           |     |        |
| Physical Examination/Vitals  | Х          | Х  |     | Х     | Х   | Х                         | Х                      | Х         | Х   | Х      |
| EKG (QTcF)                   | Х          |    |     |       |     |                           |                        |           |     |        |
| Serology HCV, HBV, CMV       | X4         |    |     |       |     |                           |                        |           |     |        |

